3. ENDPOINTS AND BASELINE VARIABLES: DEFINITIONS AND CONVENTIONS

In Stage 1, Stage 2, and Amended Stage 2, the primary and secondary endpoints assess changes in the modified CDASI *activity* and *damage* scores. The details of the calculation of these scores are presented in Section 9.2. In Stage 3, the secondary endpoints assess changes in the modified CDASI activity and damage scores *and* changes in the TIS and the components of the TIS. The details of the calculation of the TIS are presented in Section 9.8. In each stage, baseline is defined as the measurement at Day 1 (prior to dosing). Change from baseline is defined as the value at a specific visit minus the value from baseline.

Efficacy endpoint analyses may use data from a single stage or pool data across multiple stages. Stage 1 analyses will include Stage 1 data only, and Stage 3 analyses will include Stage 3 data only. Pooled analyses of data from Stage 1, Stage 2, and Amended Stage 2 will pool data from the first 12 weeks of these stages. For CCI endpoints newly added to Amended Stage 2 that were not previously included in Stage 1 or Stage 2, analyses will occur among Amended Stage 2 participants only.

Primary analysis of the CDASI activity score in Stage 1, Stage 2, and Amended Stage 2 include data from baseline to Week 12. Sensitivity and supportive analyses in these stages may include data beyond Week 12.

Secondary analysis of the TIS, components of the TIS, CDASI activity, and CDASI damage scores in Stage 3 include data from baseline to Week 12. Sensitivity and supportive analyses in these stages may include data beyond Week 12.

3.1. Endpoints in Stage 1

3.1.1. Primary Endpoint in Stage 1

• Change from baseline in CDASI activity score at Week 12.

3.1.2. Secondary Endpoint(s) in Stage 1

- Absolute values and change from baseline of CDASI activity and CDASI damage scores at all scheduled time points. Exception: The change from baseline in CDASI activity score at Week 12 is a primary endpoint.
- Incidence of adverse events (AEs), laboratory abnormalities, changes in vital signs, and electrocardiogram (ECG) findings. The extended discussion of these endpoints is presented in Section 9.3.

- Absolute values and change from baseline in the values of selected biomarkers (Gene signature panel in blood and tissue; Human Myxovirus A (MXA), interferon gamma-induced protein 10 (IP-10), IFNbeta, high sensitive C-reactive protein, (hsCRP), muscle and bone blood biomarkers, autoantibody concentrations in serum/plasma) at all scheduled time points.
- Absolute values and change from baseline in the values of PROs (the short form (SF36) Health Survey, Dermatology and Life Quality Index (DLQI), 5D Itch Scale, and physician's evaluation of disease (PhGA)) at all scheduled time points. The brief description of the scales is presented in Section 9.4.
- Absolute values and change from baseline values of the sub-scores of CDASI activity and CDASI damage scores at all scheduled time points. The description on the scores is presented in Section 9.2.

3.2. Endpoints in Stage 2

3.2.1. Primary Endpoint in Stage 2

• Change from baseline in CDASI activity score at Week 12.

3.2.2. Secondary Endpoints in Stage 2

- Absolute values and change from baseline of CDASI activity and CDASI damage scores at all scheduled times points. (Exception: The change from baseline in CDASI activity score at Week 12 is a primary endpoint).
- Incidence of adverse events (AEs) laboratory abnormalities, changes in vital signs, and electrocardiogram (ECG) findings. The extended discussion of these endpoints is presented in Section 9.3.

CCI

- Absolute values and change from baseline in the values of selected biomarkers (Gene signature panel in blood and tissue; Human Myxovirus A (MXA), interferon gamma-induced protein 10 (IP-10), IFNbeta, high sensitive C-reactive protein, (hsCRP), muscle and bone blood biomarkers, autoantibody concentrations in serum/plasma) at all scheduled time points.
- Absolute values and change from baseline in the values of PROs (the short form (SF36) Health Survey, Dermatology and Life Quality Index (DLQI), 5D Itch Scale, and physician's evaluation of disease (PhGA)) at all scheduled time points. The brief description of the scales is presented in Section 9.4.
- Absolute values and change from baseline values of the sub-scores of CDASI activity and CDASI damage scores at all scheduled time points. The description on the scores is presented in Section 9.2.

3.3. Endpoints in Amended Stage 2

3.3.1. Primary Endpoint in Amended Stage 2

• Change from baseline in CDASI activity score at Week 12.

3.3.2. Secondary Endpoints in Amended Stage 2

- Absolute values and change from baseline of CDASI activity and CDASI damage scores at all scheduled time points. (Exception: The change from baseline in CDASI activity score at Week 12 is a primary endpoint).
- Incidence of adverse events (AEs) laboratory abnormalities, changes in vital signs, and electrocardiogram (ECG) findings. The extended discussion of these endpoints is presented in Section 9.3.

- Absolute values and change from baseline in the values of selected biomarkers (Gene signature panel in blood and tissue;
- Absolute values and change from baseline in the values of the PhGA, VAS at all scheduled time points.
- Absolute values and change from baseline in the values of PROs including the Patient Global Assessment (PtGA), the Health Assessment Questionnaire Disability Index (HAQ-DI), the 5-D Pruritus Scale, CCI, the Short Form (SF-36 v2 Acute), the Dermatology and Life Quality Index (DLQI) and the European Quality of Life Five Dimension, Five Level Scale (EQ-5D-5L) & EQ Visual Analogue Scale (EQ-VAS) at all scheduled time points. The brief description of the scales is presented in Section 9.4.
- Absolute values and change from baseline values of the sub-scores of CDASI activity and CDASI damage scores at all scheduled time points. The description on the scores is presented in Section 9.2.

3.4. Endpoints in Stage 3

3.4.1. Primary Endpoint in Stage 3

• Incidence of adverse events (AEs) laboratory abnormalities, changes in vital signs, and electrocardiogram (ECG) findings. The extended discussion of these endpoints is presented in Section 9.3.

3.4.2. Secondary Endpoints in Stage 3

- Total Improvement Score (TIS) at Week 12 and intermediate scheduled time points. The description of the TIS is presented in Section 9.8.
- Change from baseline in the core Set Measures (CSM) of the TIS including PGA, PtGA, MMT, HAQ-DI, muscle enzymes, and extra-muscular activity, (MDAAT).
- Absolute values and change from baseline of CDASI activity and CDASI damage scores at all scheduled time points. The description on the scores is presented in Section 9.2.

- Absolute values and change from baseline in the values of selected biomarkers (Gene signature panel in blood; Human Myxovirus A (MXA), interferon gamma-induced protein 10 (IP-10), IFNbeta, highly sensitive C-reactive protein, (hsCRP), muscle and bone blood biomarkers, autoantibody concentrations in serum/plasma) at all scheduled time points.
- Absolute values and change from baseline in the values of the PhGA, VAS at all scheduled time points.
- Absolute values and change from baseline in the values of PROs including the Patient Global Assessment (PtGA), the Health Assessment Questionnaire Disability Index (HAQ-DI), the 5-D Pruritus Scale, CC

the Functional Assessment of Chronic Illness Therapy – Fatigue (FACIT-F), the Short Form (SF-36 v2 Acute), and the European Quality of Life Five Dimension, Five Level Scale (EQ-5D-5L) & EQ

Visual Analogue Scale (EQ-VAS) at all scheduled time points. The brief description of the scales is presented in Section 9.4.

3.5. Other Endpoints

Medical history, pregnancy testing, physical examination and recording of concomitant medications data will be analyzed according to Pfizer standard practices.

3.6. Baseline Variables

The day 1 measurements will serve as the baseline for clinical reported outcomes (CDASI Scores, Physician Global Assesment Score), patient-reported outcomes (SF36, DLQI, 5D Itch Scale), medical assessments (skin biopsies, ECG, weight, vital signs), laboratory safety measurements

Demographics and medical history data will be collected at the baseline.

4. ANALYSIS SETS

4.1. Full Analysis Set

Multiple full analysis sets are defined. They are listed briefly here and described in more detail in Sections 4.1.1 through 4.1.2.

- The Full Analysis Set (FAS) includes all subjects who received at least one dose of randomized treatment in any study stage.
- The Full Analysis Set in Stage 1 (FAS1) includes all subjects who received at least one dose of randomized treatment in Stage 1.
- The Full Analysis Set in Stage 2 (FAS2) includes all subjects who received at least one dose of randomized treatment in Stage 2.
- The Full Analysis Set in Amended Stage 2 (FASA2) includes all subjects who received at least one dose of randomized treatment in Amended Stage 2.

- The Full Analysis Set in Stage 1 and Stage 2 (FAS12) includes all subjects who received at least one dose of randomized treatment in Stage 1 or Stage 2.
- The Pooled Full Analysis Set, skin cohort (PFASS) includes all subjects who received at least one dose of randomized treatment in Stage 1, Stage 2, or Amended Stage 2.
- The Full Analysis Set in Stage 3 (FAS3) includes all subjects who received at least one dose of randomized treatment in Stage 3.
- The Pooled Full Analysis Set, fixed sequence stages (PFASF) includes all subjects who received at least one dose of randomized treatment in Amended Stage 2 or Stage 3.

4.1.1. Full Analysis Sets in Stage 1, Stage 2, and Amended Stage 2

The FAS1 is defined as all subjects who have received at least one dose of randomized treatment in Stage 1. This is the primary analysis population for the safety and treatment compliance in Stage 1. In the analyses it is assumed that subjects are assigned to the randomized treatment regardless of what treatment was received. Note that Section 9.2 of the protocol references a modified intent to treat (mITT) set. In Stage 1, the mITT set in Stage 1 is synonymous with the FAS1 mentioned in this document.

The FAS2 is defined as all subjects who have received at least one dose of randomized treatment in Stage 2. This is the primary analysis population for the safety and treatment compliance in Stage 2.

The FAS12 is defined as all subjects who have received at least one dose of randomized treatment in Stage 1 or Stage 2. The FAS12 may be used for analyses assessing the durability of response for subjects in Stage 1 or Stage 2.

The FASA2 is defined as all subjects who have received at least one dose of randomized treatment in Amended Stage 2. This analysis population will be used only for endpoints unique to Amended Stage 2 that were not collected in other stages.

The PFASS is defined as all subjects who have received at least one dose of randomized treatment in Stage 1, Stage 2, or Amended Stage 2. This is the primary analysis population for the safety and treatment compliance across Stage 1, Stage 2, and Amended Stage 2. In the analyses it is assumed that subjects are assigned to the randomized treatment regardless of what treatment was received. Note that Section 9.2 of the protocol references a mITT set. The mITT set for Stage 1, Stage 2, and Amended Stage 2 is synonymous with the PFASS mentioned in this document.

4.1.2. Full Analysis Sets in Stage 3

The FAS3 is defined as all subjects who have received at least one dose of randomized treatment in Stage 3. This is the primary analysis population for the safety and treatment compliance in Stage 3. In the analyses it is assumed that subjects are assigned to the randomized treatment regardless of what treatment was received. Note that Section 9.2 of

the protocol references a mITT set. In Stage 3, the mITT set in Stage 3 is synonymous with the FAS in Stage 3 mentioned in this document.

The PFASF is defined as all subjects who have received at least one dose of randomized treatment in Amended Stage 2 or Stage 3. The PFASF may be used for analyses assessing the durability of response for subjects with baseline CDASI activity score of 14 or greater in Amended Stage 2 or Stage 3.

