7.13. Shipment of Pharmacokinetic Samples

The shipment address and contact information will be provided to the investigator site prior to the initiation of the study. The central laboratory will provide collection materials and directions for packaging and shipment of samples and will forward samples to the contract analytical laboratory. The contract analytical laboratory will be provided with randomization codes so that only samples in the PF-06823859 treatment groups are assayed. Placebo samples may be assayed in the event of suspected error in participant randomization. Refer to the central laboratory manual for further information.

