8.5. Medication Errors

Medication errors may result from the administration or consumption of the investigational product by the wrong participant, or at the wrong time, or at the wrong dosage strength Medication errors include:

- Medication errors involving participant exposure to the investigational product;
- Potential medication errors or uses outside of what is foreseen in the protocol that do or do not involve the participating participant.

Such medication errors occurring to a study participant are to be captured on the medication error page of the CRF, which is a specific version of the AE page.

In the event of a medication dosing error, the sponsor should be notified immediately.

Whether or not the medication error is accompanied by an AE, as determined by the investigator, the medication error is recorded on the medication error page of the CRF and, if applicable, any associated AE(s), serious and non-serious, are recorded on an AE page of the CRF.

Medication errors should be reported to Pfizer Safety within 24 hours on a CT SAE Report Form **only when associated with an SAE**.

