4.3. Safety Analysis Set

Multiple safety analysis sets are defined.

- The safety analysis set (SAS) includes all subjects who received at least one dose of randomized treatment in any stage.
- The safety analysis set in Stage 1 (SAS1) includes all subjects who received at least one dose of randomized treatment in Stage 1.
- The safety analysis set in Stage 2 (SAS2) includes all subjects who received at least one dose of randomized treatment in Stage 1 or Stage 2.
- The safety analysis set in Amended Stage 2 (SASA2) includes all subjects who received at least one dose of randomized treatment in Amended Stage 2.

• The safety analysis set in Stage 3 (SAS3) includes all subjects who received at least one dose of randomized treatment in Stage 3.

Subjects who are not treated will be excluded from the safety analysis.

- In Stage 1, the biomarker analysis population is defined as all enrolled subjects in Stage 1 who received at least one dose of PF-06823859 with at least one biomarker assessment.
- For Stage 1, Stage 2, and Amended Stage 2, the biomarker analysis population is defined as all enrolled participants in Stage 1, Stage 2 and Amended Stage 2 who received at least one dose of PF-06823859 with at least one biomarker assessment.
- In Stage 3, the biomarker analysis population is defined as all enrolled participants in Stage 3 who received at least one dose of PF-06823859 with at least one biomarker assessment.

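### The SAP names two competing families of safety population, and its only rule for attributing safety events is by randomised arm, whatever was received

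*SAP*

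**What the plan says.** SAP 4.1.1 says of FAS1: "This is the primary analysis population for the safety and treatment compliance in Stage 1". The next sentence gives an allocation rule: "In the analyses it is assumed that subjects are assigned to the randomized treatment regardless of what treatment was received". The same pair of statements appears for the pooled skin-cohort set PFASS ("This is the primary analysis population for the safety and treatment compliance across Stage 1, Stage 2, and Amended Stage 2") and, in SAP 4.1.2, for FAS3 ("This is the primary analysis population for the safety and treatment compliance in Stage 3"). FAS2 is also named for safety ("This is the primary analysis population for the safety and treatment compliance in Stage 2"), but no allocation sentence follows it.

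SAP 4.3 then defines a second family: SAS, SAS1, SAS2, SASA2 and SAS3. The Stage 1 definition is typical: "The safety analysis set in Stage 1 (SAS1) includes all subjects who received at least one dose of randomized treatment in Stage 1". None of these definitions says whether participants are grouped by assigned or by actual treatment. Protocol 9.4 has its own safety population, which is anyone given any study drug or placebo, and 9.4.1 places the adverse event and suicidality analyses in it. Neither section gives a grouping rule.

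SAP 6.7.1 plans three sets of adverse event tables: Stage 1; Stages 1, 2 and Amended 2 together; and Stage 3. SAP 6.7.1 to 6.7.4 name no analysis set. The laboratory, vital sign and ECG summaries are by treatment or dose group, without saying which treatment is meant. SAP 9.3.1 defines treatment emergence relative to a given treatment and does not say whether that is the one assigned or the one received.

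**The concern.** Grouping by randomised arm is right for efficacy because it preserves the randomised comparison. A safety table answers a different question: what happened to people exposed to the product. If a participant receives something other than the assigned product, the as-randomised rule credits any event to a product or dose that did not precede it.

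The protocol foresees such errors. Section 8.5 lists "administration or consumption of the investigational product by the wrong participant, or at the wrong time, or at the wrong dosage strength", and section 7.13 provides that "Placebo samples may be assayed in the event of suspected error in participant randomization". Under Protocol 5.4.2 doses are prepared by unblinded site staff, and from Stage 2 they handle two active strengths as well as placebo.

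Safety and tolerability is a secondary objective in Stage 1, Stage 2 and Amended Stage 2, and the primary objective in Stage 3. Protocol 1.5.1 already reports an apparently higher rate of mild upper respiratory infection on drug, and Appendix 17.5 notes a potential viral-infection risk. With arms this small, a single misplaced participant is visible in a table.

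**Working it through.** The plan states no figure for this point, so there is none to reproduce. The check is a comparison of texts, followed by simple arithmetic on size.

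**Step 1. Match each planned adverse event table to a named set.**

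| Adverse event table (SAP 6.7.1) | Set in SAP 4.1 | Grouping rule there | Set in SAP 4.3 | Grouping rule there |
|---|---|---|---|---|
| Stage 1 | FAS1 | as randomised | SAS1 | none |
| Stages 1, 2 and Amended 2 | PFASS | as randomised | no match | none |
| Stage 3 | FAS3 | as randomised | SAS3 | none |

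In SAP 4.3, SAS2 covers Stage 1 or Stage 2, SASA2 covers Amended Stage 2 only, and SAS covers every stage including Stage 3. The union of SAS2 and SASA2 would fit the second table, but it is not defined. PFASS is the only named set that fits.

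**Step 2. Compare membership.** Every full analysis and safety set in the SAP requires a dose of the randomised treatment. Protocol 9.4 requires only a dose of study drug or placebo. Read literally, a participant given nothing but the wrong product falls outside the SAP sets but inside the protocol's safety population.

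**Step 3. Size of one misattributed participant.** Inputs from SAP 2.2:

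- Stage 1: 32 randomised 2:1, so 32/3 ≈ 11 placebo and about 21 on 600 mg.
- Stage 2: about 20 randomised 5:11:4, so 5 on 600 mg, 11 on 150 mg and 4 placebo.
- Pooled: 32 + 20 = 52, with 11 + 4 = 15 placebo, 21 + 5 = 26 on 600 mg and 11 on 150 mg.

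Suppose an arm of n includes one misdosed participant with an event, and k of the others also have the event. As randomised, incidence is (k+1)/n. With that participant moved out it is k/(n−1). The difference is (n−1−k)/[n(n−1)], which is largest at k = 0, where it equals 1/n:

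- Stage 1 placebo: 1/11 = 9.1 points
- 150 mg: 1/11 = 9.1 points
- pooled placebo: 1/15 = 6.7 points
- pooled 600 mg: 1/26 = 3.8 points

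The shift is smaller for commoner events. With n = 11 and k = 3 it is 7/110 = 6.4 points.

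**Step 4. Effect on the contrast.** Suppose one Stage 1 placebo participant received active drug throughout and had the only event of its kind. As randomised, the rates are 1/11 = 9.1% on placebo and 0/21 = 0% on active. By treatment received, they are 0/10 = 0% and 1/22 = 4.5%. The sign of the difference reverses.

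**Step 5. Sensitivity to pooled size.** SAP 2.2 gives about 76 participants overall and 8 to 16 in Stage 3, leaving 60 to 68 for the skin stages. That is 8 to 16 more than 52, with no stated split. If the extra participants also followed 5:11:4 (an assumption), 150 mg would be 11 + 0.55×8 = 15.4 to 11 + 0.55×16 = 19.8, and placebo 15 + 0.2×8 = 16.6 to 15 + 0.2×16 = 18.2. The shifts would then be about 6.5 to 5.1 points for 150 mg and 6.0 to 5.5 points for pooled placebo.

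**The case against.** A reader might infer that the SAP has settled on an as-randomised safety analysis. The documents do not support that. SAP 4.3 and Protocol 9.4 and 9.4.1 set up a separate safety population. For FAS1, PFASS and FAS3 the as-randomised sentence sits beside a note equating the set with the protocol's mITT population, which Protocol 9.2 defines for efficacy. The safety sections of the SAP name no set. They also defer to sponsor reporting standards that are not in the documents and might contain an as-treated convention. This stands: what the documents show is a conflict with only one stated rule, not a settled choice.

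Three other inferences go too far.

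- The problem is not confined to Stages 1 and 2. FAS2 lacks the as-randomised sentence, so the rule reaches Stage 2 through PFASS. FAS3 carries it.
- One could quote 1/4 = 25 points for the Stage 2 placebo group of 4, but no adverse event table for Stage 2 alone is planned.
- The distortion does not always favour the drug. A 150 mg participant wrongly given 600 mg who has an event makes 150 mg look worse.

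It is also fair to say that the harm is conditional and partly detectable. Medication errors go on a dedicated CRF page with or without an adverse event (Protocol 8.5), and SAP 6.6.3 summarises doses of active and control by treatment group. SAP 6.7.1 describes safety analysis as generally exploratory. These outputs would reveal an error, but they would not move the event to the right column of the adverse event table.

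**Conclusion.** The point holds as a conflict over which population the safety tables use, combined with an attribution rule unsuited to safety. As-randomised is the only rule stated, no as-treated rule appears in either document, and for the pooled skin-cohort table the one matching set carries the as-randomised rule.

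The shift per misattributed participant with an event is up to about 9 points in Stage 1 placebo or 150 mg, and about 7 points in placebo pooled over 52. This assumes exact allocation, no other events of that kind in the arm, and 20 participants in Stage 2; a larger skin cohort makes the pooled figures smaller. The documents give no misdosing rate, and without a dosing error nothing changes. Stage 3 is not sized because each participant is planned to receive both products. How events are laid out around the planned Week 12 switch is a separate matter.

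This should be corrected, but it does not threaten the trial's conclusions.

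**What to change.** In SAP 4.3:

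- Name one safety set for each adverse event reporting group: Stage 1; pooled Stages 1, 2 and Amended 2; and Stage 3. State in SAP 6.7 that all safety summaries use these sets.
- Define membership as in Protocol 9.4, by any dose of study drug or placebo, so that a wholly misdosed participant is not lost.
- Classify participants by treatment actually received.
- Pre-specify how to classify anyone given a mix of correct and incorrect infusions, since each treatment course has three. For example, any active dose received in a placebo period could count as active. The rule must also cover a mix of 150 mg and 600 mg.

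In SAP 4.1.1 and 4.1.2, remove safety from the statements for FAS1, FAS2, PFASS and FAS3. Keep as-randomised allocation for efficacy.

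The cost is SAP wording and a derived actual-treatment variable. Dose records and the medication-error page already hold the data, and no design or sample size changes. Because Stage 1 data were reviewed at the interim analysis, the amendment should say whether any Stage 1 participant is reclassified.
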